18.1.1 SIDE EFFECTS

Reported toxicity of ruxolitinib includes the following:

- Hematologic adverse events include; anemia, thrombocytopenia and neutropenia, all of which are dose related effects.
- Non-hematologic adverse events include; bruising, dizziness, headache, raised ALT, raised AST, hypercholesterolemia, urinary tract infections, weight gain, flatulence, herpes zoster, increase in systolic blood pressure, constipation, infection, including Tuberculosis

18.2 ENASIDENIB

Enasidenib tablets are available in 50-, 100-, 150- and 200-mg free-base equivalent strength tablets for oral administration. Each tablet is formulated using excipients that are generally regarded as safe and are used in marketed drug products. Celgene Corporation will supply 50-mg and 100-mg tablets.

All tablets will be packaged in high density polyethylene (HDPE) bottles with a desiccant (silica gel) canister and child resistant closures with heat induction seal. All tablets should be swallowed whole and should not be broken or chewed.

Bottles of enasidenib tablets must be stored according to the package label. The storage area should be secure and have limited access. Enasidenib tablets will be monitored by the Sponsor for stability for the duration of the study.

18.2.1 SIDE EFFECTS

Reported specific adverse drug reactions of enasidenib includes the following:

- Hematologic adverse events include: neutropenia and leukocytosis
- Non-hematologic adverse events include: IDH-DS

TLS, GI disturbances (such as nausea, diarrhea, vomiting, and associated dysgeusia and decreased appetite), and hyperbilirubinemia.

A Phase II Open-label Study of Combined Ruxolitinib and Enasidenib Sinai in Patients with Accelerated/Blast-phase Myeloproliferative Neoplasm or Chronic-

phase Myelofibrosis with an IDH2 Mutation

(Myeloproliferative Neoplasms Research Consortium [MPN-RC] 119)

18.2.2 STUDY DRUG PACKAGING AND LABELING

Enasidenib tablets will be supplied in high density polyethylene (HDPE) bottles with a desiccant (silica gel) canister, a polyester coil, and child resistant closures with heat induction seal. Packaging and labeling will be prepared to meet all regulatory requirements.

18.2.3 STUDY DRUG STORAGE

MPN-RC

Bottles of enasidenib tablets must be stored according to the package label.

All study drug products must be stored in a secure, limited-access location and may be dispensed only by the Investigator or by a member of the staff specifically authorized by the Investigator.

18.2.4 RECEIVING DRUG SUPPLY, RECEIPT AND STORAGE

Drug will be distributed from Celegene to each participating site. Tablets are to be stored according to guidance in drug label insert.

18.2.5 RETURN OR DESTRUCTION OF STUDY DRUG

Destruction of any remaining study drug will occur according to Mount Sinai Investigational Drug Services' standard operating procedures.

18.3 RISKS TO SUBJECTS

Adverse events listed in current investigational brochures research medications:

Both ruxolitinib and enasidenib have known side effects profile in patients with myelofibrosis and AML respectively. Please refer to to the investigator brochures for detailed listings.

Known potential side effects from **Ruxolitinb** in humans include the following:

Hematologic: Anemia (72% to 96%; Grade 3: \leq 34%; Grade 4: \leq 11%), Thrombocytopenia (27% to 70%; Grade 3: 5% to 9%; Grade 4: \leq 4%), Neutropenia (3% to 19%; Grade 3: 5%; Grade 4: \leq 2%) all of which are dose-related effects.

Non-hematologic: Dizziness (15% to 18%), Headache (15% to 16%), Fatigue (15%), Insomnia (12%), Weakness (7%), Bruise (23%), Epistaxis (6%), Pruritus (14%), Increased serum cholesterol (17% to 35%), Hypertriglyceridemia (15%). Diarrhea (15%), Abdominal pain (15%), Constipation (8%), Nausea (6%), Flatulence (5%), Vomiting. Increased serum ALT (25%; Grade 3: <1%), Increased serum AST (17% to 23%). Muscle spasm (12%); Weight gain (\leq 7%). Dyspnea (13%), Edema (8%), Hypertension (<6%). Infection including: Urinary tract infection (\leq 9%), Herpes zoster (2% to 6%), Nasopharyngitis (9%), Cough (8%).

Known potential side effects from **Enasidenib** in humans include the following:

Non-hematologic: IDH-DS (14%), Noninfectious leukocytosis (8.2%), TLS (5.5%), GI disturbances Nausea (50%), Diarrhea (43%), Decreased appetite (34%), Vomiting (34%), Dysgeusia (12%), Hyperbilirubinemia (81%). In addition, Febrile neutropenia (23.9%), Pneumonia (14.2%), Sepsis (11.8%), Pyrexia (8.5%), Lung infection (6.4%), Acute renal failure (5.5%), and Fatigue (5.2%)

Based on available pharmacokinetic and drug metabolism data, there are no anticipated major adverse reactions that may manifest secondary to drug-drug interactions when enasidenib is utilized concomitantly with ruxolitinib; however, there is a potential for unforeseeable adverse events with the combination.

A Phase II Open-label Study of Combined Ruxolitinib and Enasidenib Sinai in Patients with Accelerated/Blast-phase Myeloproliferative Neoplasm or Chronicphase Myelofibrosis with an IDH2 Mutation

(Myeloproliferative Neoplasms Research Consortium [MPN-RC] 119)

18.3.1 REPRODUCTIVE RISKS

MPN-RC

Patients should not become pregnant or father a baby while on this study. Women should not breastfeed a baby while on this study. Females of childbearing potential must either commit to continued abstinence from heterosexual intercourse or begin TWO acceptable methods of birth control, one highly effective method and one additional effective method AT THE SAME TIME, at least 4 weeks before she starts taking study medications (enasidenib and ruxolitinib). Females of childbearing potential must also agree to ongoing pregnancy testing. Men must agree to use a condom during sexual contact with a female of child bearing potential even if they have had a successful vasectomy. All patients must be counseled at a minimum of every 28 days about pregnancy precautions and risks of fetal exposure.

Pregnancies and suspected pregnancies (including a positive pregnancy test regardless of age or disease state) of a female subject occurring while the subject is on IP, or within (4 months), are considered immediately reportable events. IP is to be discontinued immediately. The pregnancy, suspected pregnancy, or positive pregnancy test must be reported to Celgene Drug Safety immediately by facsimile, or other appropriate method, using the Pregnancy Initial Report Form, or approved equivalent form. The female subject may be referred to an obstetrician-gynecologist (not necessarily one with reproductive toxicity experience) or another appropriate healthcare professional for further evaluation.

The Investigator will follow the female subject until completion of the pregnancy, and must notify Celgene Drug Safety immediately about the outcome of the pregnancy (either normal or abnormal outcome) using the Pregnancy Follow-up Report Form, or approved equivalent form.

If the outcome of the pregnancy was abnormal (e.g., spontaneous or therapeutic abortion), the Investigator should report the abnormal outcome as an AE. If the abnormal outcome meets any of the serious criteria, it must be reported as an SAE to Celgene Drug Safety immediately by facsimile, or other appropriate method, within 24 hours of the Investigator's knowledge of the event using the SAE Report Form, or approved equivalent form.

All neonatal deaths that occur within 28 days of birth should be reported, without regard to causality, as SAEs. In addition, any infant death after 28 days that the Investigator suspects is related to the in utero exposure to the IP should also be reported to Celgene Drug Safety immediately by facsimile, or other appropriate method, within 24 hours of the Investigator's knowledge of the event using the SAE Report Form, or approved equivalent form.

Male Subjects

If a female partner of a male subject taking investigational product becomes pregnant while the male subject is on study treatment or within 4 months of the male subject's last study treatment, the male subject taking IP should notify the Investigator, and the pregnant female partner should be advised to call their healthcare provider immediately.

CORRELATIVES/ SPECIAL STUDIES

Submission of samples for correlative studies is mandatory. The correlative biomarker studies will evaluate a series of biomarkers at baseline (at study entry), and during treatment at each study visit, and either at the time of relapse/progression or at termination of study (that is off study drug for any reason). Please see Table 5 for various time points for collection of samples.

19.1 SHIPPING INSTRUCTIONS

in Patients with Accelerated/Blast-phase Myeloproliferative Neoplasm or Chronicphase Myelofibrosis with an IDH2 Mutation

(Myeloproliferative Neoplasms Research Consortium [MPN-RC] 119)

Each site will provide the necessary shipping materials to package.Blood and bone marrow samples will be shipped at room temperature on the day of collection. All shipments must be sent by overnight courier for delivery before 10 AM or morning delivery the next day. Nail may be sent with the ambient shipment on the day of collection. Slides may be batched and shipped every 3 months. In general shipments cannot be received on Saturday. For special arrangements, contact [name] prior to collection of tissue and shipment.

[name], Ph. D New York Blood Center [name] [contact] [contact] [contact] Laboratory [contact] Laboratory [contact] [contact]

SAMPLES ARE ACCEPTED MONDAY-THURSDAY 9AM TO 5PM; FRIDAY 9AM TO 1PM.

NOTE:SAMPLES CANNOT BE RECEIVED ON SATURDAY OR SUNDAY. CALL [name] BEFORE COLLECTING SAMPLES IF SPECIAL ARRANGEMENTS NEED TO BE MADE.

Include a de-identified copy of the institutional bone marrow aspiration and biopsy report with your shipment to the NYBC in New York. This report must include MPN-RC patient ID number, differential cell counts on the marrow aspirate, if performed. Contact the central office with any questions.

19.2 BONE MARROW BIOPSY SLIDES GUIDELINES

The following samples are to be collected at screening, at baseline, at Cycle 4 Day 1 (at the discretion of the Investigator for chronic phase patients), at Cycle 7 Day 1, Cycle 10 Day 1 (at the discretion of the Investigator for chronic phase patients), after every 6 cycles thereafter, and at termination of study for any reason. Biopsies should be done to confirm complete response and when clinically indicated. The following bone marrow aspiration and biopsy specimens must be obtained and submitted to [name] at the New York Blood Center:

- three (3) air-dried, unstained bone marrow aspirate slides (if available)
- four (4) unstained peripheral blood films (thin smears)
- two (2) air dried unstained bone marrow biopsy touch preps for patients with no aspirate sample (these are made with 8 touches per slide 4 horizontal touches in 2 rows on the slide)

Additionally:

MPN-

- three (3) unstained paraffin-fixed bone marrow biopsy slides each containing at least 2 sections
- one (1) stained H & E biopsy slide
- one (1) biopsy slide stained for iron
- one (1) biopsy slide stained with the silver for reticulin fibrosis stain should be submitted for confirmatory cytologic and cytochemical studies. These should be submitted together with the final institutional pathology, cytochemistry, and immuno-phenotyping reports (if possible)

Bone marrow biopsy should be repeated if relapse occurs or transformation to MDS, or acute leukemia is suspected.

There must be an adequate amount of marrow biopsy specimen in each smear. The above requirements are considered minimal.

in Patients with Accelerated/Blast-phase Myeloproliferative Neoplasm or Chronicphase Myelofibrosis with an IDH2 Mutation

(Myeloproliferative Neoplasms Research Consortium [MPN-RC] 119)

Identify each slide with the subject's patient ID number, protocol number, time point, and type of sample.

The histopathology slides may be batch shipped every 3 Months to [name] at the NY Blood Center.

Identify each slide with the patient's MPN-RC patient ID number, protocol number, time point, and type of sample.

Include a de-identified copy of the institutional bone marrow aspiration and biopsy report with your shipment to the NYBC in New York. This report must include MPN-RC patient ID number, differential cell counts on the marrow aspirate, if performed.

19.3 BONE MARROW ASPIRATE GUIDELINES

Bone marrow aspirate samples will be collected for histopathology, biomarkers, and cytogenetics/FISH. For biomarkers and cytogenetics, obtain a total of 3-7 mL of aspirated bone marrow. Apirate samples collected for biomarkers will be sent to the NYBC on the day of collection. Aspirate samples collected for cytogenetics/FISH will be sent to each site's local labs for analysis. Samples are to be divided as follows:

- 2-5 mL of bone marrow aspirate in a green top, heparinized tube (BD catalog number 366480)
- 1-2 mL of bone marrow aspirate for Cytogenetics

In the event that a biopsy does not produce aspirate, additional perpipheral blood samples must be sent for cytogenetic/FISH analysis.

19.4 PERIPHERAL BLOOD: (USE STERILE TECHNIQUE)

Peripheral blood samples will be collected at screening, and day 1 of Cycle 1-Cycle 7, every 3 cycles, and at the end of study, in conjunction with standard-of-care blood draws. The total amount to be collected should not exceed 25cc (approximately 5 teaspoons). Peripheral blood samples must be shipped ambient on the day of collection.

• 25 mL of blood: three ACD (yellow top) tubes (BD catalogue number 364606; 8.5 mL tubes)

19.5 NAIL CLIPPINGS

MPN-RC

Two to ten nail clippings are to be obtained from each patient during the initial entry onto the protocol. Clippings are to be placed in a paper envelope and the envelope is to be sealed. The sealed envelope maybe stored and shipped at room temperature.

19.6 CYTOGENETIC ANALYSIS

Diagnostic and follow up cytogenetics will be performed by local institutional laboratories. All karyotypes will be centrally reviewed (see below). Samples are to be sent for cytogenetic analysis at screening, at cycle 4 day1, cycle 7 day 1, cycle 10 day 1, every 6 cycles thereafter, and at termination of study for any reason. JPEG or TIFF images must be uploaded into the MPN-RC REDCap database for each cytogenetic assessment. To ensure uniformity of cytogenetic preparations all participating local laboratories must adhere to the following requirements established by the central karyotype review co-Investigator ([name]).

A Phase II Open-label Study of Combined Ruxolitinib and Enasidenib Sinai in Patients with Accelerated/Blast-phase Myeloproliferative Neoplasm or Chronic-

phase Myelofibrosis with an IDH2 Mutation

(Myeloproliferative Neoplasms Research Consortium [MPN-RC] 119)

19.6.1

MPN-RC

GENERAL INCLUSION CRITERIA FOR CONVENTIONAL CYTOGENETICS

- 1. Banding level 300 or more and structural aberrations are accepted at 400 or higher banding level or confirmed by FISH.
- 2. Minimum requirements for baseline assessments: From each patient, bone marrow (PV, ET) and or unstimulated PB (PMF) specimen must be set up into two, preferably three, different cultures (direct, 24 hrs. with and without marrow max media). Every effort should be made to obtain the growth of cells that are cytogenetically abnormal.
- 3. 20 metaphase evaluated from two or more cell cultures or from marrow max culture only.
- 4. Only G-banding of chromosomes is acceptable. Other banding methods are not acceptable.
- 5. Analysis of cell at 300 band resolution, or low-quality banding, irrespective of the findings, to be complemented with FISH screening for subtle aberrations, including del(20)(q11q13) with D20S108 probe.
- 6. ISCN 2009 must be used to describe the karyotype.
- 7. Aberrations classified as clonal should be present in at least 2 cells by G-banding or confirmed by FISH.
- 8. Unusual or novel findings should be fully characterized by FISH using appropriate probes.
- 9. Three karyotypes (and metaphase cells) from each patient must be uploaded electronically into the MPN-RC REDCap database to document the stated cytogenetic diagnosis. The karyotypes are uploaded either as TIFF or JPEG files.

FISH studies, IF POSSIBLE and warranted in an individual case

- 1. Case normal by G banding, if possible, ought to be screened for cryptic changes by interphase FISH using a MPN panel of 12 probes: CEP1(1q12)/1q21, 5p15.2/5q31(EGR1), CEP7/7q31, CEP8, CEP9/9p21, RB1 at 13q14, P53/CEP17, 20q12/D20S108.
- 2. FISH studies are performed on BM or PB on interphase cells processed directly (no culture) using Abbott Molecular FISH probes. A minimum of 200 cells at baseline should be scored by two individuals. Image of FISH results should be uploaded as JPEG or TIFF file into the MPN-RC database.

Central Karyotype Review: [name]., Director, Tumor Cytogenetics, Icahn School of Medicine, NY.

One of the **QC indicators** is a proper entry and submission of cytogenetic forms and karyotypes by the institutional cytogenetic laboratories. If the local laboratory fails two consecutive specimens (poor quality of chromosome banding, missed abnormality, wrong ISCN nomenclature) or lack of entering cytogenetic results into MPN- RC, the laboratory will be informed, and the third failure will result in placing the local laboratory on probation and the institutional PI will be informed. If required, either the central lab in NY or other MPN-RC approved cytogenetic lab will perform the studies from the institution whose cytogenetic lab is placed on probation.

For any questions please call [name] PhD, Cytogenetic Research Coordinator, Mount Sinai Medical Center: **[contact]** or [name] at **[contact]**.

19.7 SPECIMEN BANKING

Subject samples collected for this study will be retained at New York Blood Center. Specimens will be stored indefinitely or until they are used up. If future use is denied or withdrawn by the subject, best efforts will be made to stop any additional studies and to destroy the specimens.

The MPN-RC Consortium's Tissue Distribution Committee will be responsible for reviewing and approving requests for clinical specimen from potential research collaborators outside of the

in Patients with Accelerated/Blast-phase Myeloproliferative Neoplasm or Chronicphase Myelofibrosis with an IDH2 Mutation

(Myeloproliferative Neoplasms Research Consortium [MPN-RC] 119)

Consortium. Collaborators will be required to complete an agreement (a Material Transfer Agreement or recharge agreement) that states specimens will only be released for use in disclosed research.

The specimens, DNA, and their derivatives may have significant therapeutic or commercial value. The Informed Consent form contains this information and informs the subject that there is the potential for financial gain by the Investigator or a collaborating researcher or entity. Genetic testing is a plan for future research.

The following information obtained from the subject's medical record may be provided to research collaborators when specimens are made available:

- Diagnosis
- Collection time in relation to study treatment
- Clinical outcome if available
- Demographic data

Sampling times may be adjusted according to early trial results in order to optimize evaluation. No additional samples will be collected without formal amendment to this protocol. Detailed procedures for collection, handling, and shipment of samples will be provided in the study Laboratory Manual.

Samples will be sent to special laboratories at the New York Blood Center for careful study and analysis where they will be store using a unique code. The code linking the sample will be stored at Mount Sinai and known only to members of the research team at the Central Coordinating Office.

Table 5. Correlative Studies Sample Collection Schedule

	Sample		Baseline	Cycle 1-6 Day 1	Cycle 4, 7, 10, day 1 and every 3 cycles ⁴	End of study ⁵
	Aspirate Histopathology	Three (3) air dried unstained slides	Х		Х	Х
row	Aspirate Cytogenetics ²	At local institution, upload data and karyotypes to the website ¹ . If no aspirate, provide peripheral blood karyotypes.	Х		Х	Х
	Aspirate Biomarkers ³	2 to 5 mL of bone marrow aspirate in a green top, heparinized tube (BD catalog #366480)	Х		Х	Х
one Ma	Biopsy Histopathology	One (1) H&E stain	Х		Х	Х
ă		One (1) Iron stain	Х		Х	Х
		One (1) Silver impregnated reticulin stain	Х		Х	Х
		Three (3) Unstained paraffin- fixed slides each with at least 2 sections	Х		Х	Х

The Tisch Cancer Institute

A Phase II Open-label Study of Combined Ruxolitinib and Enasidenib Sinai

in Patients with Accelerated/Blast-phase Myeloproliferative Neoplasm or Chronicphase Myelofibrosis with an IDH2 Mutation

	(Myclopio	miciative recipiasins research)
	Sample		Baseline	Cycle 1-6 Day 1	Cycle 4, 7, 10, day 1 and every 3 cycles ⁴	End of study ⁵
		If no aspirate, two (2)air dried unstained touch preps, 8 touches/slide, 2 horizontal	х		Х	Х
	Histopathology	Four (4) Unstained peripheral blood films, thin smears	Х		Х	Х
l Blood	Cytogenetics ²	If no BM aspirate karyotypic analysis ¹	Х		Х	Х
Periphera	Biomarkers ³	Three (3) ACD: yellow (BD# 364606; 8.5 mL)	Х	Х	Х	X
Other	Nails	2 to 10 clippings (pre-treatment, at enrollment only)	X			

(Myeloproliferative Neoplasms Research Consortium [MPN-RC] 119)

- All slides MUST BE LABELED properly. Labels are to include the patient's ID number, protocol number, time of study (e.g., baseline), type of specimen (e.g., BM biopsy, BM aspirate, blood), type of stain (e.g., Iron, H& E). For unstained slides, use a pencil to label the slides. All slides are to be sent to [name] at the NYBC in a labeled slide box. The label on the box is to include the patient's ID, protocol number, and time of study.
- 2. Cytogenetic analyses are performed as a standard of care. Karyotypic analysis of unstimulated bone marrow after direct 24 and 48 hours, if available, or peripheral blood shall be performed. Karyotypic analysis using G-banding technology is required.
- 3. All tissue samples must be registered via the MPN-RC on-line Patient Registration system (https://redcap2.mayo.edu/redcap/ the day they are collected and prior to shipment. All tubes, and envelopes (nails) must be labeled with patient's ID number, protocol number, time of study (e.g. baseline), type of specimen (e.g. BM biopsy, BM aspirate, blood) and date of collection.
- 4. BMB is optional for cycles 4 and 10 at the discretion of the Investigator for chronic phase patients
- 5. At relapse/progression or termination of study drug (that is off study drug for any reason).

Fresh blood and bone marrow are to be stored at ambient temperature and must be shipped on the day that they are collected.

Nails are to be stored at ambient temperature and may be shipped with the fresh specimens or subsequently.

All slides are to be shipped to the tissue bank laboratory in a labeled slide box. The label on the box is to include the patient's ID, protocol number, and time point of study. Slides may be shipped in batches together with the local institution's histopathology report, every 3 months. All slides are shipped to [name] [name] at the address above.

20. STATISTICAL CONSIDERATIONS

STUDY DESIGN/STUDY ENDPOINTS

This is a Phase II design to evaluate the efficacy of ruxolitinib and enasidenib combination therapy for accelerated or blast-phase MPN patients with IDH2 mutations. The study will also include a descriptive cohort of up to 9 evaluable patients with chronic phase MPN and will utilize a Gehan design in this cohort. This study will be the first time ruxolitinib and enasidenib will be used in combination for this patient population. Therefore, the safety of the combination will be confirmed in the first six patients

MPN-RC

in Patients with Accelerated/Blast-phase Myeloproliferative Neoplasm or Chronicphase Myelofibrosis with an IDH2 Mutation

(Myeloproliferative Neoplasms Research Consortium [MPN-RC] 119)

who are enrolled in the study. If no more than one patient out of the initial six has a treatment-related Grade 3 or higher adverse event attributable to the study drugs, the combination therapy will be considered safe. If more than one patient out of the initial six has a limiting toxicity the trial will be suspended, and the safety data will be further reviewed.

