3. STUDY SCHEMA

Eligible patients with signed consent who have completed all requisite screening tests and procedures are to start Cycle 1 Day 1 within 30 days of signing consent.

All adverse events captured during the first 28 days of treatment with Ruxolitinib and Enasidenib will be used to assess safety and tolerability in the first 6 patients on study.

Cycles will be a minimum of 28 days.

Following cycle 6, response will be assessed by IWG/ELN consensus criteria and patients will continue treatment if response was deemed a CR/CRi/PR or CBR for MPN-AP and MPN-BP patients. For chronic phase MF, response will include CR/PR and clinical improvement.

Patients will continue to be followed post treatment for long term survival every 3 months for up to 12 months by telephone encounter or medical record review to determine the following variables: alive versus deceased and type of current therapy.

*Ruxolitinib dosing based on platelet counts; Enasidenib 100 mg for MPN-AP or MPN-BP and 50 mg for chronic phase MF for cycle 1

in Patients with Accelerated/Blast-phase Myeloproliferative Neoplasm or Chronicphase Myelofibrosis with an IDH2 Mutation

(Myeloproliferative Neoplasms Research Consortium [MPN-RC] 119)

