(Myeloproliferative Neoplasms Research Consortium [MPN-RC] 119)

observed, or at the discretion of the treating physician. Patients will have an end of study visit for a safety follow-up at 30 days after their last dose of therapy.

10.1 DOSE MODIFICATION FOR NON-HEMATOLOGICAL AE'S, CLINICALLY SIGNIFICANT IN THE OPINION OF THE TREATING PHYSICIAN

Based on available pharmacokinetic and drug metabolism data, ruxolitinib is mainly metabolized by CYP3A4 with additional contribution from CYP2C9. Enasidenib inhibits CYP2C9 and induces CYP3A4. Although no adjustment is recommended when ruxolitinib is co-administrated with CYP3A4 inducer, potential drug-drug interactions might occur. This study will be the first time ruxolitinib and enasidenib will be used in combination for this patient population. Therefore, the safety of the combination will be confirmed in the first six patients who accrue. If no more than one patient out of the initial six has a treatment-related Grade 3 or higher adverse event attributable to the study drugs, the combination therapy will be considered safe. If more than one patient out of the initial six has limiting toxicity, the trial will be suspended, and the safety data will be further reviewed.

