11.4 PATIENT ACCRUAL

MPN-RC

Subjects are considered evaluable as long as they have signed informed consent, are eligible for participation and started study treatment. The maximum sample size in the Phase II (accelerated/blast-phase) is 20 evaluable patients. Allowing for enrollment of up to 2 additional patients to account for ineligibility, cancellation, major treatment violation, or other reasons, this study will enroll a maximum of 22 patients in the Phase II AP/BP cohort. The maximum sample size in the chronic phase MPN is 9 evaluable patients. Allowing for enrollment of up to 1 additional patient, this study will enroll a maximum of 10 patients in the descriptive chronic phase MPN cohort. Therefore, a maximum total of 32 (22 + 10) patients will be enrolled in the trial.

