21. SAMPLE SIZE AND ACCRUAL

The maximum sample size in the Phase II (accelerated/blast-phase) is 20 evaluable patients. Allowing for enrollment of up to 2 additional patients as replacements for unevaluable patients (ineligibility, cancellation, major treatment violation, or other reasons), this study will enroll a maximum of 22 patients in the Phase II AP/BP cohort. The maximum sample size in the chronic phase MPN is 9 evaluable patients. Allowing for enrollment of up to 1 additional patient as replacement for unevaluable patients, this study will enroll a maximum of 10 patients in the descriptive chronic phase MPN cohort. Therefore, a maximum total of 32 (22 + 10) patients will be enrolled in the trial.

The anticipated accrual rate is approximately 2-3 patients per month. Therefore, the accrual period for this study is expected to be 15 months. The primary analysis can begin approximately 21 months after the trial begins, i.e., as soon as the last patient has been observed for 6 cycles.

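### The six-patient safety rule has a fixed denominator and no provision for treated patients who leave before day 28, so incomplete observation makes it easier to pass

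*Combined protocol and SAP*

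**What the plan says.** The rule appears in three places, each with a different word for its population.

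- Section 20 states that "the safety of the combination will be confirmed in the first six patients". After a page header that splits the sentence in the text, the population and the pass limit follow: "who are enrolled in the study. If no more than one patient out of the initial six has a treatment-related Grade 3 or higher". Within that limit on events attributed to the study drugs, the combination is considered safe. On the other side: "If more than one patient out of the initial six has a limiting toxicity the trial will be suspended". A further look at the safety data follows.
- Section 10.1 repeats the rule, but there "the safety of the combination will be confirmed in the first six patients who accrue".
- Section 3 (Study Schema) supplies the observation window, since what is recorded "during the first 28 days of treatment with Ruxolitinib and Enasidenib will be used to assess safety and tolerability in the first 6 patients". Here the six are those *on study*.

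The population is therefore the first six who are *enrolled*, who *accrue*, or who are *on study*. No section defines a patient who is evaluable for toxicity, sets a minimum exposure or follow-up for this decision, provides replacement within the six, or says when the review takes place.

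The only general definition is in Section 11.4: "Subjects are considered evaluable as long as they have signed informed consent, are eligible for participation and started study treatment". It asks for no minimum follow-up. Section 21 allows "replacements for unevaluable patients (ineligibility, cancellation, major treatment violation, or other reasons"), but for the cohort sample sizes and not for the safety decision.

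**The concern.** The rule counts events out of a fixed six. Take a patient who starts both drugs and then withdraws, progresses or dies of disease in the second week, with no treatment-related Grade 3 or higher event. That patient is evaluable under Section 11.4, keeps a slot in the denominator, and can add nothing more to the numerator. Read literally, one event in six then means one event among fewer than six completed windows.

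The efficacy rule runs the other way. Under Section 20.1 an evaluable patient who does not meet the response definition is a non-response, so incomplete data count against the regimen. Under the safety rule incomplete data count in its favour.

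At stake is the only numerical safety rule in the plan, for a combination that the protocol says has not been used before in this population. Passing it labels the combination safe.

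**Working it through.** **Figure to reproduce.** None. The documents give no target toxicity rate, pass probability or error rate for this rule.

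**Inputs.** From Sections 10.1 and 20: pass if 0 or 1 of six has a qualifying event. From Section 3: a 28-day window. Assumed: a true 28-day event rate *p* of 20%, 33%, 40% or 50%, and one or two of the six not fully observed.

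**Step 1. All six observed.** P(pass) = (1−p)^6 + 6p(1−p)^5. At p = 0.33: 0.0905 + 0.2673 = 0.358.

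**Step 2. One or two give no information but hold their slots.** Only n = 5 or n = 4 patients can produce an event, so P(pass) = (1−p)^n + np(1−p)^(n−1). At p = 0.33:

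- n = 5: 0.1350 + 0.3325 = 0.468
- n = 4: 0.2015 + 0.3970 = 0.599

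**Step 3. One patient observed for half the window.** With constant hazard, that patient's event probability is h = 1 − √(1−p), which is 0.1815 at p = 0.33. The rule passes if the other five have no event, or if they have exactly one and this patient has none: 0.1350 + 0.3325 × 0.8185 = 0.407.

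Probability of passing:

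| True rate (assumed) | Six fully observed | One observed half the window | One gives no information | Two give no information |
|---|---|---|---|---|
| 20% | 65.5% | 69.4% | 73.7% | 81.9% |
| 33% | 35.8% | 40.7% | 46.8% | 59.9% |
| 40% | 23.3% | 27.9% | 33.7% | 47.5% |
| 50% | 10.9% | 14.2% | 18.8% | 31.2% |

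**Step 4. Are incomplete windows plausible?** Section 6.1 cites historical blast-phase median survivals from 2.6 months to 6–7 months. Assume exponential survival and take 28 days as 0.92 months. Then P(death before day 28) = 1 − 0.5^(0.92/median).

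- Median 2.6 months: 0.217. At least one of six: 1 − 0.783^6 = 0.77.
- Median 7 months: 0.087. At least one of six: 1 − 0.913^6 = 0.42.

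This is an upper-end range. It treats all six as blast-phase, although accelerated- and chronic-phase patients are also eligible (Section 8.1). A death attributed to treatment would count as an event and not as lost observation. Withdrawal and progression are not included.

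**The case against.** **Untreated patients.** A reader might infer from *enrolled* that patients who never received a dose count among the six as event-free. The documents do not support that as a rule. Section 3 counts days of treatment. Section 10 gives accelerated- and blast-phase patients enasidenib on enrolment. Section 11.4 requires that treatment has started, and Section 22.2 limits adverse event rates to eligible patients who started it. Section 21 lists cancelled patients as unevaluable. Registration does precede treatment (Section 14.2.1), so the wording could be tighter, but this is a lesser ambiguity.

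**Silence is not a scoring rule.** No section says that a patient with an incomplete window is scored as safe. That is correct. The effect follows from the fixed denominator together with the absence of any exclusion or replacement.

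**Early leavers still inform.** They are observed until they leave, and an earlier qualifying event counts. The columns for no information are therefore the extreme case, and the half-window column shows the milder one. Attribution also narrows the gap: under Section 16.3 the only unrelated category is for events clearly not related, so an early death escapes the count only if the investigator clearly excludes the drugs.

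**The 42–77% range is not a forecast.** A reader might take it as what this trial should expect. The series are retrospective, and the trial applies performance-status and organ-function limits. With the 9.3-month median that Section 6.3 gives for enasidenib in relapsed or refractory AML, a different disease, the same formula gives 6.6% and about 34% for at least one of six.

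**Other safeguards.** Failing the rule leads to suspension and review, not closure. Serious events are notified within 24 hours (Section 17.2), toxicity is discussed in monthly teleconferences (Section 26.13), and a DSMB provides quarterly safety reports (Section 24.1). These limit the consequence. They do not say who belongs among the six.

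**Conclusion.** The concern holds for treated patients who do not complete the 28-day window. The plan fixes the denominator at six, words the population three ways, and neither requires a completed window nor replaces a patient without one. Where leaving is not itself a qualifying event, the lost observation can only make passing easier.

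At an assumed 33% true rate, the pass probability rises by about 5 percentage points (35.8% to 40.7%) if one patient is seen for half the window. It rises by 11 points (to 46.8%) or 24 points (to 59.9%) if one or two give no information. At 50% the corresponding figures are 10.9%, 14.2%, 18.8% and 31.2%. The toxicity rates, the number of incomplete windows and the constant hazard are all assumptions. The documents give none of them.

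The documents do not support the stronger reading that untreated patients are deliberately counted as safe.

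**What to change.** Reconcile Sections 3, 10.1 and 20 with one definition of the population for this decision: the first six patients who received both drugs and either completed 28 days of observation or had a qualifying event earlier. Replace the others for this decision only. They stay in the efficacy analysis and in the adverse event tables as now planned. State that the review takes place when the sixth such patient becomes evaluable, and list each replaced patient with the reason, so that the review can see whether leaving was related to tolerability.

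The cost is wording, and possibly one or two more patients before the review. At the stated accrual of 2–3 patients per month that is about 0.3 month (1 ÷ 3) to 1 month (2 ÷ 2) of accrual, plus their own 28 days. The cohort sizes and the Simon and Gehan rules do not change.
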